### ***Other information on consent***

The requirements of the relevant ethics committee will be adhered to at all times. Should there be any subsequent amendment to the final protocol, which might affect a participant's participation in the trial, continuing consent will be obtained using an amended consent form, which will be signed by the participant.

Where the patient is being assessed and treated via telemedicine (as is often standard care in many stroke services out of hours) by a member of the medical team who is appropriately trained and listed on the delegation log, the process is as above, with the exception that the paper consent form will be countersigned by a witness unconnected with the study and signed by the investigator upon their return to the hospital site. If the patient does not wish to decide via telemedicine they will not be enrolled. This process has been successfully used in TICH-2 study (Ref: ISRCTN93732214).

If needed, the usual hospital interpreter and translator services will be available to assist with discussion of the trial, the participant information sheets, and consent forms, for follow up consent. Due to the rapid consent process, interpreters will not be used for verbal consent. The consent forms and information sheets will not be available in other languages.

It will be explained to the potential participant or their relative/friend that entry into the trial is entirely voluntary and that their treatment and care will not be affected by their decision. It will also be explained that they can withdraw at any time. In the event of their withdrawal, it will be explained that their data collected so far cannot be erased and we will seek consent to use the data in the final analyses where appropriate.

## TRIAL / STUDY TREATMENT AND REGIMEN

Trial treatment is administered as transdermal glyceryl trinitrate 5 mg patches. Sham treatment comprises a Duoderm dressing. Both are covered with a gauze dressing

Participants will be assessed in hospital (see flow chart)

- Before treatment on day 0.
- 1 hour after treatment on day 0.
- 1 hour after treatment on day 1.
- At discharge/death.

Follow up at day 90 will be via a telephone interview (as in ENOS, RIGHT-2). Researchers will not contact the participant or their family directly at day 90; they will first contact the participant's general practitioner (GP) or obtain information through the Medical Research Information Service/NHS Information Centre to check their health status. Permission to contact the GP at day 90 will be sought at the time of consent. In the event that a participant has been unable to be contacted to perform their follow-up at day 90, researchers will send a letter to their GP to request that they (or another healthcare professional if more appropriate), confirm an appropriate mRS value for the participant and the date on which this value was determined. This aims to reduce data loss associated with participants being lost to follow up.

Brain imaging (CT head scan) will be performed at baseline (Day 0):

- As part of routine clinical management prior to or soon after enrolment – all acute stroke patients have a CT head scan performed on admission to hospital for diagnostic purposes, this including a non-contrast CT scan +/- CT angiogram.

### Participant measures

Assessments	Screen	Day 0 Baseline Pre-treatment	Day 0 Post-treatment	Day 1: During treatment	Day 2: after treatment	Discharge, death	Day 90: Telephone
Face-to-face							
Clinical assessment	X 				X	X	
Eligibility screen	X						

CT Scan		X 	or X 				
Consent		X		or X	or X		
Randomisation		X					
GTN/Sham patch			X	X			
mRS		X 					
U&E FBC		X 					
Blood pressure		X 	X	X			
NIHSS		X 			X		
DSRS		X			X		
Blood Biomarkers		X 			X 		
Hospital utilisation						X 	
Listed events				X 	X 		
SAEs, non-fatal			X	X	X		
SAEs, fatal				X	X	X	X
mRS							X
Barthel Index							X
EuroQoL (EQ5D)							X
Cognition (t-MMSE, TICS)							X
Mood (ZDS)							X

CT: Computerised tomography

NIHSS: National Institutes of Health stroke scale

MMSE: mini mental state examination

mRS modified Rankin scale

SAEs: serious adverse events

1. Routine as part of clinical practice

2. Pre-morbid mRS

3. Biomarkers: soluble markers, genetics

4. Open-label blood pressure lowering, intravenous thrombolysis, mechanical thrombectomy, hyperacute stroke unit, Stroke Rehabilitation Unit, physiotherapy, occupational therapy, speech & language therapy, surgery for IS – hemicraniectomy, surgery for ICH, days in intensive/critical care unit.

5. Hypotension, hypertension, headache, infection

6. mRS, BI, EQ-5D, EQ-VAS, t-MMSE, TICS and ZDS scales are given in Appendices A-H.

7. Neuroimaging scales are listed in Appendices I and J.

### Concomitant and Rescue Medications and Treatments

The intervention (GTN or sham) will be given in addition to routine care. There are no prohibited concomitant treatments.

No publications have been found that would suggest a contraindication as a result of the interaction between the IMP and the COVID-19 vaccine.

## **Compliance**

Compliance will be assessed by examining the participant's drug chart and recording evidence of treatment administration. Adherence will be recorded on the case report forms after treatment has been completed (day 2).

## **Accountability for drugs & placebos**

The pharmacist will maintain records of the dispensing of the IMP from pharmacy to stroke unit/ED and the clinical and research team will record administration of the IMP to the patient. Dispensing details will be recorded on each participant's CRF. Unused and partially used supplies will be returned to pharmacy. This will be recorded in the pharmacy study log.

## **Management of study drug overdose**

No specific antidotes are available. The study drug is administered as a transdermal patch by qualified nursing/medical staff so the potential for overdose is not anticipated.

## **Urgent Safety Measures**

Any urgent safety measure relating to a Clinical Trial of an Investigational Medicinal Product (CTIMP) should be communicated to the MHRA immediately. They advise that sponsors phone the MHRA Clinical Trial Unit and discuss the event with a safety scientist. The sponsor must then follow-up with notification in writing within three days of the action being taken. The notification should be in the form of a substantial amendment and should describe the event, the measures taken and justification for the measures taken. Please see the section on adverse event reporting.

## **Protocol Deviations and Violations**

The study should be conducted in accordance with the approved protocol and changes to the protocol will only be made to protect the safety, rights, or welfare of the subject.

### **Protocol Deviation**

A Protocol Deviation is a deviation from the protocol that affects the conduct of the trial in a usually minor way. This includes any deviation from the trial protocol that is not listed as a Protocol Violation.

### **Protocol Violation**

A protocol violation is a usually major deviation from the expected trial regimen such as where a participant is enrolled in spite of not fulfilling all the inclusion and exclusion criteria, or where deviations from the protocol could affect the trial delivery or interpretation significantly.

All protocol deviations and violations must be reported immediately to the Chief Investigator, via the online electronic case report form. The CI will notify the Sponsor if a deviation or violation has an impact on participant safety or integrity of the trial data. The Sponsor will advise on appropriate measures to address the occurrence, which may include reporting of a serious GCP breach, internal audit of the trial and seeking counsel of the trial committees.

Examples of protocol violations are given below but this list is not exhaustive:

- Day 2 follow-up performed >7 days past due date

- Death/discharge form entered >14 days after event
- Day 90 follow-up performed <80 days or >120 days past due date
- Participant enrolled in spite of not fulfilling all the inclusion and exclusion criteria
- Aneurysmal subarachnoid haemorrhage known at time of randomisation
- Non-stroke diagnosis, known at time of randomisation
- Failure to complete SAEs where appropriate
- Management of IMP – treatment pack lost

### Criteria for terminating trial

The trial may be terminated by either the TSC, the sponsor or the funder if there is overwhelming evidence of major safety concerns, new information becomes available that makes the trial unsafe or irrelevant, or there are issues with trial conduct (e.g., poor recruitment, loss of resources).

## RADIATION EXPOSURE

### Details of diagnostic or therapeutic ionising radiation

Participants will have 1 or more CT head scans:

- **Clinical:** A routine clinical CT head scan comprising non-contrast CT shortly after presentation to hospital according to the local clinical imaging protocol; this may be performed before or immediately after trial treatment has been initiated. This CT head scan is part of routine clinical care and is independent of the trial. For patients who are randomised into the trial the scan and results will be used as baseline data.
- **Clinical:** Patients may need additional head CT scans performed for clinical reasons (e.g., deterioration or stroke recurrence); scans and reports from these will also be collected for the study.

These approaches were used in the ENOS and RIGHT-2 trials

### Details of radioactive materials and dose

1 CT Brain – 2 mSv (utilising mean DLP from recent national survey by Public Health England ref. PHE-CRCE-013 (2014) and conversion co-efficient from Shripton et. al. British Journal of Radiology 89 (2016)). This leads to the following maximum protocol dose; 1 CT Head – 2 mSv

### Risk Assessment (induction of fatal cancer)

This study requires exposures to ionising radiation. The total protocol dose is 2mSv. This is equivalent to approximately 1 year of background radiation in the UK.

Ionising radiation can cause cancer which manifests itself after many years or decades. The risk of developing cancer as a consequence of taking part in this study is approximately 0.01%. For comparison, the natural lifetime cancer incidence in the general population is about 50%.

The doses involved are too small to cause direct radiation tissue effects such as erythema or epilation.

### Clinical Assessment

The scan itself takes about half a minute and does not involve any injections. The scan uses x-rays, which in large amounts can be harmful, but for this extra CT head scan the additional risk to the participant from the scan has been judged to be extremely small.

The objective of the exposure is to assess the extent of the bleeding (haematoma) in the brain to see if it has got worse (larger) or better (smaller) following treatment. An alternative would be MRI brain scan, but this takes longer, and many patients are unsuitable or unable to tolerate it due to claustrophobia.

The procedure for CT and any doses in lay terms are explained in the participant information sheet.

## **TRANSPORT AND STORAGE OF THE TISSUES**

### **University of Nottingham**

#### ***Genetic studies***

Genetic samples will be taken from participants to help understand the causes of stroke, the relationship with treatment effect and predictors of outcome. Consent will be taken for genetic sampling either at baseline (Day 0) or Day 2. The patient or relative/friend may request destruction of the genetic samples at any time after consent and prior to analysis.

After analysis, all samples will be used to exhaustion or destroyed in accordance with HTA guidance. These tests will be performed for research only and the results will not be fed back to the clinical team.

#### **Local hospital site (Urea and electrolytes, Full blood count)**

Blood samples for urea and electrolytes and full blood count will be taken at baseline as part of routine clinical practice and on day 2 after the end of treatment. Samples will be labelled in accordance with local NHS procedures and will be analysed according to the local NHS procedures. These results will be available for the clinical and research teams.

The master database will be held by University of Nottingham on a dedicated research server in a password encrypted file.

## **LABORATORY ANALYSES**

Analysis of routine clinical blood samples will be performed by the recruiting site. Analysis of research blood samples will take place at the University of Nottingham (Division of Clinical Neuroscience).

Blood samples will be collected at the local site as below and processed in accordance with the trial SOPs

After the study ends all samples will be used to exhaustion or destroyed in accordance with HTA guidance. These tests will be performed for research only and the results will not be fed back to the clinical team.

### ***Soluble markers of outcome and efficacy***

Several blood biomarkers are surrogate markers of outcome, such as S-100 and neurone specific enolase. Which biomarkers will be assayed will be determined after the trial has finished collecting samples and will be based on the latest scientific knowledge on which biomarkers are the most useful predictors of outcome and efficacy.

### ***Genetic studies***

An important aim of the genetic analyses is to determine whether polymorphic differences in candidate genes explain blood pressure and outcome responses to GTN (pharmacogenetic analysis). Which genotyping will be performed will be determined after the trial has finished collecting samples and will be based on the latest scientific knowledge on which analyses are the most useful predictors of outcome and efficacy. Likely analyses will include genes related to the synthesis and metabolism of nitric oxide (e.g., endothelial nitric oxide synthase) and the mechanism of action of antihypertensive agents (e.g., polymorphisms in receptors).

### ***Procedure if blood samples cannot be processed***

In circumstances where no appropriately trained members of the research team are available to process blood samples, these tests should be omitted. Participants may still be randomised and treated with the IMP but without these laboratory tests.

## **STATISTICS and DATA MANAGEMENT PLAN**

### **DATA MANAGEMENT PLAN**

This document describes the procedures for the management and assurance of quality of all data collected within a trial throughout the life cycle of the trial from CRF design through to publication of the data, long-term storage, and data sharing. The Sponsor's Standard Operating Procedure will be followed for data management.

#### **General**

The Trial Management Committee will include the Trial Programmer and Trial Statistician who are based in the Nottingham Stroke Trials Unit (see Trial Personnel and Contact Details, page 2). The Trial Programmer will design, programme, and maintain the trial system comprising an electronic case report form (eCRF), web front-end, and database. Access to the database will be via an encrypted web application and password access.

Monitoring of trial data shall include confirmation of informed consent; source data verification; data storage and data transfer procedures; local quality control checks and procedures, back-up and disaster recovery of any local databases and validation of data manipulation. The Trial Coordinator, or where required, a nominated designee of the Sponsor, shall carry out monitoring of trial data as an ongoing activity.

Entries on eCRFs will be verified by inspection against the source data. A sample of CRFs (10% or as per the trial risk assessment) will be checked on a regular basis for verification of all entries made. In addition, the subsequent capture of the data on the trial database will be checked. Where corrections are required, these will carry a full audit trail and justification.

Trial data and evidence of monitoring and systems audits will be made available for inspection by the regulatory authority as required.

In compliance with the ICH/GCP guidelines, regulations and in accordance with the University of Nottingham Code of Research Conduct and Research Ethics, the Chief or local Principal Investigator will maintain all records and documents regarding the conduct of the study. These will be retained for at least 7 years or for longer if required. If the responsible investigator is no longer able to maintain the study records, a second person will be nominated to take over this responsibility.

The Trial Master File and trial documents held by the Chief Investigator on behalf of the Sponsor shall be finally archived at secure archive facilities at the University of Nottingham. This archive shall include all trial databases and associated meta-data encryption codes.

### **Data Capture and Data Queries**

Data will primarily be captured using electronic CRFs entered through an online web application, with paper versions of the same forms available for completion when required. Instructions for investigators to complete online CRFs will be included in the training slides given at site initiation, with detailed information provided by working practice documents. A demonstration site/database will also be available for investigators to practice using the system.

Data queries will be tracked online by the issue tracker, with warnings shown to investigators and shown on the data queries report. In addition to data queries identified by the trial statistician and programmer, staff in the co-ordinating office can also raise and close issues that they identify.

Protocol violations will be submitted online, primarily by site investigators, and evaluated by the chief investigator who will determine if a serious GCP breach has occurred or not in each case.

### **Description of Data Entry Validation**

The trial programmer will identify required validation for each question on each CRF and it will be applied when each form is submitted, prior to the record being stored. These validation checks will be documented against the CRF itself for use by the trial statistician. The trial statistician will automate additional data checks and submit any exceptions found into the online issue tracker

### **Data Cleaning and Database Lock**

Prior to each database lock, the trial managers/trial co-ordinators will chase outstanding data queries and the lock will take place in accordance with the documented data lock procedure once notification has been given to the trial programmer by the chief investigator. Both interim and final locks will be documented and primarily consist of the creation of a read-only copy of the live database, with each copy available to the trial statistician via the online data extract process.

### **Monitoring**

Monitoring of trial data shall include confirmation of informed consent; source data verification; data storage and data transfer procedures; local quality control checks and procedures, back-up and disaster recovery of any local databases and validation of data

manipulation. The Trial Coordinator, or where required, a nominated designee of the Sponsor, shall carry out monitoring of trial data at site up to three times during the period of the study unless issues are highlighted warranting further visits. Monitoring of consent forms and electronic data input will be an ongoing process for the duration of the trial.

## **STATISTICS**

### **Methods**

Data will be analysed by a qualified statistician who is blinded to treatment allocation, using a validated software package. A statistical analysis plan (SAP) will be agreed prior to database lock and release of randomisation codes. The trial will be reported in accordance with CONSORT guidelines including the extension to pilot and feasibility trials, as appropriate.

This is a feasibility trial, and the main analysis will be with descriptive statistics; comparisons between treatment groups will also be performed. Results will be summarised and analysed as follows:

- Counts will be summarised using frequency and percentage (N, %) and compared with binary logistic regression.
- Time to event analyses will be summarised using frequency and percentage (N, %) and compared with Cox proportional hazards regression.
- Ordered categorical variables will be summarised using median [interquartile range] and compared with ordinal logistic regression.
- Continuous variables will be summarised using mean (standard deviation) and compared with multiple linear regression.

We will assess the feasibility of recruiting, treating, and following up patients from 2 centres over three years. We will estimate a recruitment rate, treatment rate and follow-up rate. It is likely that a large definitive trial would be feasible if at least 75 participants were recruited into this study, that compliance with randomised treatment was high and that a high proportion of follow up data was available. Lower recruitment would not preclude progression if there was evidence that the barriers to recruitment identified could be overcome.

### **Sample size and justification**

Since this is a feasibility study with one of the objectives being to determine potential recruitment rates, a formal sample size calculation is not appropriate. If more than 75 participants are randomised from 2 centres over a 31-month period, it is likely that a larger study recruiting approximately 500 participants in around 20 centres would be feasible. Depending on the final sample size calculation for the definitive study, the number of centres and recruitment period could be determined using the information from the rates and patterns observed in the feasibility study.

### **Assessment of efficacy**

This is a feasibility trial and as such will have no formal assessment of efficacy. The proposed primary efficacy outcome in a definitive trial would be death or dependency at day 90, measured using the modified Rankin scale. Shifts in this scale will be summarised for this trial but no formal confirmatory statistical analyses will be performed. Similarly, all other efficacy variables will be summarised using descriptive statistics.

## **Assessment of safety**

Serious adverse events will be summarised using descriptive statistics according to the treatment the participant received.

## **Procedures for missing, unused and spurious data**

Missing data will be reported. The investigation of this data and methods implemented to address the missing data, if appropriate, will be detailed in the SAP.

## **Definition of populations analysed**

All available data will be used including overall numbers of patients presenting in clinic and screening data (where available).

Where summaries by treatment group are provided, these will be based on an intention to treat population i.e., according to the treatment the participant was randomised to, with the exception of safety data.

A safety population will be defined to summarise the safety data in this study. Participants will be summarised according to the treatment they received irrespective of randomisation.

Summaries of the proportion of participants who would form a per protocol population in a larger trial, and reasons for exclusion from a per protocol population will be provided, to allow future planning. No data will be summarised on this population.

## **ADVERSE EVENTS**

### **Definitions**

#### **Adverse events**

An adverse event is any unfavourable and unintended sign, symptom, syndrome, or illness that develops or worsens during the period of observation in the study.

An AE does include a / an:

1. Exacerbation of a pre-existing illness.
2. Increase in frequency or intensity of a pre-existing episodic event or condition.
3. Condition detected or diagnosed after medicinal product administration even though it may have been present prior to the start of the study.
4. Continuous persistent disease or symptoms present at baseline that worsen following the start of the study.

These will not be collected since >4000 patients with hyperacute and acute stroke have been studied in previous trials and GTN has been therapeutically used for >150 years. However, a number of events that may be expected to occur during or shortly after administration of GTN, i.e. an adverse drug reaction, will be collected prospectively:

1. Hypotension requiring intervention (such as raising the legs, administration of intravenous fluids, cessation of open-label hypotensive therapy, or removal of the IMP/sham).

2. Hypertension requiring intervention (such as administration of open-label hypotensive therapy).
3. Headache
4. Infection (such as involving the respiratory or urinary tract).

An AE does not include a / an:

1. Medical or surgical procedure (e.g., surgery, endoscopy, tooth extraction, transfusion); but the condition that led to the procedure is an AE.
2. Pre-existing disease or conditions present or detected at the start of the study that did not worsen.
3. Situations where an untoward medical occurrence has not occurred (e.g., hospitalisations for cosmetic elective surgery, social and / or convenience admissions).
4. Disease or disorder being studied or sign or symptom associated with the disease or disorder unless more severe than expected for the participant's condition.
5. Overdose of concurrent medication without any signs or symptoms.

A **Serious Adverse Event (SAE)** is any adverse event occurring following study mandated procedures, having received the IMP or placebo that results in any of the following outcomes:

1. Death
2. A life-threatening adverse event
3. Inpatient hospitalisation or prolongation of existing hospitalisation
4. A disability / incapacity
5. A congenital anomaly in the offspring of a participant

Important medical events that may not result in death, be life-threatening, or require hospitalisation may be considered a serious adverse event when, based upon appropriate medical judgment, they may jeopardize the patient or participant and may require medical or surgical intervention to prevent one of the outcomes listed in this definition

All adverse events will be assessed for seriousness, expectedness, and causality:

A distinction is drawn between serious and severe AEs. Severity is a measure of intensity whereas seriousness is defined using the criteria above. Hence, a severe AE need not necessarily be serious.

Serious adverse events are common in stroke; a full list of expected SAEs that are not subject to expedited reporting are given in Appendix K.

As the IMP is administered once and has a short half-life, serious adverse events occurring within the first 2 days will be assessed for seriousness, expectedness, and causality. In addition, fatal SAEs will be reported until day 90.

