Outcome measures	
Feasibility outcome
 
 
Recruitment of 100 IS patients, 20 ICH patients
 
 
Mechanistic outcomes
 
 
Blood pressure (BP) and heart rate (HR) over first 2 days
 
Bloods
 
 
Clinical outcomes
 
Day 2
 
 
Impairment
 
 
Discharge or death
 
 
Discharge destination
 
 
Day 90
 
 
Functional outcome: modified Rankin Scale (mRS = primary clinical outcome)
 
Disability (Barthel index, BI), cognition (telephone TICS, MMSE), mood (Zung depression scale, ZDS), quality of life (Euro-QoL EQ-5D and EQ-VAS).
 
 
Safety outcomes
 
 
Serious adverse events (SAEs) up to day 2 (i.e., 48 hours after 1st patch applied; fatal SAEs to day 90.
 
Death
 

Statistical methods	
This is a feasibility trial, and the main analysis will be with descriptive statistics only. Counts will be summarised using N and %, and continuous variables will be summarised using means (standard deviation) or median [interquartile range] depending on their distribution. Mechanistic, clinical and safety outcomes will be compared between the treatment groups using binary logistic regression, Cox proportional hazards regression (death), ordinal logistic regression (mRS) or multiple linear regression (BI, TICS, t-MMSE, ZDS, EQ-5D, EQ-VAS, as appropriate, in exploratory analyses.

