## DETAILS OF INVESTIGATIONAL MEDICINAL PRODUCT(S)

### Description

The investigational medicinal product (IMP) is transdermal glyceryl trinitrate patch (GTN, - Transiderm-Nitro '5' (Novartis). GTN is also known as nitroglycerin (NTG). One patch will be given on 2 consecutive days. Further chemical and pharmacological properties of the GTN patch - Transiderm-Nitro '5' are provided in a separate Summary of Product Characteristics document (SmPC).

The GTN patch will be placed on the shoulders or back and the position rotated daily. GTN patches will be covered with a gauze dressing to mask the patient to treatment.

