## **TRIAL / STUDY DESIGN**

### **TRIAL CONFIGURATION**

Prospective parallel-group randomised sham-controlled phase II feasibility and safety trial of GTN versus sham given initially between 3 and 5 hours after stroke, and then at 09.00 on the next day.

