### **Safety endpoints**

#### By day 2

- Any serious adverse event.
- Headache.
- Infection (pneumonia/chest, urinary tract, other).
- Hypotension requiring clinical intervention.
- Hypertension requiring clinical intervention.

#### From day 3 to day 90

- Any fatal serious adverse event.

Data on stroke recurrence and acute coronary syndrome, termed safety outcome events, will be collected up to day 90.

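### The two-day limit on non-fatal SAEs is justified by a single administration, but two patches are given, so follow-up after the second is 15 to 39 hours (minor)

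*Protocol*

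**What the plan says.** The Protocol (Adverse events, Definitions) gives the reason for the window: "As the IMP is administered once and has a short half-life, serious adverse events occurring within the first 2 days will be assessed". It then extends reporting of fatal SAEs to day 90.

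The regimen is described differently elsewhere. The IMP Description says "One patch will be given on 2 consecutive days". Trial configuration says treatment is "given initially between 3 and 5 hours after stroke, and then at 09.00 on the next day". The Participant measures table marks its "GTN/Sham patch" row on both Day 0 and Day 1.

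The Synopsis supplies the clock: "Serious adverse events (SAEs) up to day 2 (i.e., 48 hours after" the first patch. Safety endpoints (Protocol, and SAP 24c) list SAEs, headache, infection, hypotension and hypertension by day 2 without an hour count, and only fatal SAEs after that. They add: "Data on stroke recurrence and acute coronary syndrome, termed safety outcome events, will be collected up to day 90".

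**The concern.** A short half-life supports a short window after the last dose. It does not support starting the clock at the first dose when a second follows the next morning. The Protocol describes its prospectively collected events as "a number of events that may be expected to occur during or shortly after administration of GTN", and that reasoning applies to the second patch as much as to the first.

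The trial is presented as a feasibility and safety trial, and general adverse events are not collected. Non-fatal SAEs are therefore a substantial part of the harm record. At stake is whether that record covers the second patch adequately for everyone. If the second patch is worn for about a day, the window could close while some participants are still wearing it. That fits poorly with the Participant measures table, where the last non-fatal SAE collection falls in a Day 2 column headed as after treatment.

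**Working it through.** The 48 hours is a definition, so the plan has no calculated figure to reproduce. The check is clock arithmetic.

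Inputs:
- First patch at clock hour t on the enrolment day, 0 ≤ t < 24. Eligibility limits time since onset (3 to 5 hours) but not the time of day.
- Second patch at 09.00 next day, which is clock hour 24 + 9 = 33 (Trial configuration).
- Non-fatal SAE window of 48 hours from the first patch (Synopsis).

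Formulas:
- Gap between patches = 33 − t.
- Capture after patch 2 = 48 − (33 − t) = 15 + t. This is below 24 only if t < 9.
- Proposed limit, counted from patch 1 = max(48, 33 − t + 24) = max(48, 57 − t).
- Added collection = max(0, 9 − t).

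| First patch | Gap (h) | Capture after patch 2 now (h) | Proposed limit from patch 1 (h) | Added (h) |
|---|---|---|---|---|
| 00.00 | 33 | 15 | 57 | 9 |
| 02.00 | 31 | 17 | 55 | 7 |
| 06.00 | 27 | 21 | 51 | 3 |
| 09.00 | 24 | 24 | 48 | 0 |
| 17.00 | 16 | 32 | 48 | 0 |
| just before 24.00 | just over 9 | just under 39 | 48 | 0 |

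Who is affected: with treatment at 3 to 5 hours, a first patch between 00.00 and 09.00 implies onset between 19.00 (00.00 − 5 h) and 06.00 (09.00 − 3 h), or a wake-up stroke.

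Wear time: none is stated for patch 2. Assuming about 24 hours, it comes off at clock hour 57, which is 57 − t hours after patch 1. For t < 9 the window then closes (57 − t) − 48 = 9 − t hours before removal, so up to 9 hours.

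Alternative reading, with day 2 as a calendar day: if enrolment is day 0 (Participant measures), day 2 ends at clock hour 72 and capture after patch 2 is 72 − 33 = 39 hours for everyone. If randomisation is day 1 (Duration of the trial), day 2 ends at hour 48 and capture is 48 − 33 = 15 hours for everyone. The Synopsis definition is the only one given in hours, so it is used here.

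**The case against.** The strongest reply is that only one phrase is wrong and no harm follows. Every participant given patch 2 on schedule has at least 15 hours of capture after it, well beyond the 1 to 2 hour peak quoted in the Background. No passage sets a minimum after patch 2, so the 24-hour benchmark is a reviewer's choice. If patch 2 is worn for 24 hours, the proposed limit gives those first treated before 09.00 no capture after removal, and it replaces a common window with one that varies by participant. All of this stands, and it keeps the point minor.

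A reader might infer more than the documents support:
- That related SAEs after 48 hours would be lost. Reporting of adverse events asks participants to contact the site about any SAE, and neither that section nor the SUSAR section states a two-day limit.
- That the listed events are cut off in the same way. The hour count in the Synopsis is attached to SAEs only. The listed events are due by day 2 without one, so the shortfall is shown for SAEs alone.
- That many participants are affected. The consent section does foresee out-of-hours work ("Where the patient is being assessed and treated via telemedicine (as is often standard care in many stroke services out of hours"), but out of hours includes evenings, when capture after patch 2 is longest. It does not establish how many first patches go on before 09.00.
- That the comparison between arms is biased. Assessment of safety calls the SAE summary descriptive, whereas SAP 25c and Tables 8 and 9 plan regressions and p-values, so the analysis is not purely descriptive. The same window nevertheless applies to both arms.

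**Conclusion.** The stated rationale is factually wrong and should be corrected. Under the Synopsis definition, non-fatal SAE capture after the second patch is 15 to 39 hours, and under 24 hours only for first patches before 09.00. Early closure, by up to 9 hours before removal, depends on the assumed wear of about 24 hours. The inconsistent day numbering means that sites could apply a different limit from the one computed here.

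The consequence is small. Fatal SAEs, stroke recurrence and acute coronary syndrome are followed to day 90, and the primary endpoint and sample size are untouched. The number of participants affected cannot be derived from the documents.

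Separately, SAP Table 8 heads its left panel as SAEs to day 90, although non-fatal SAEs are collected only to day 2. Read as printed, two-day counts could be mistaken for 90-day totals.

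Severity: minor. The arithmetic is firm; the benchmark is a judgement.

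**What to change.** - Protocol, Adverse events (Definitions): replace the single-administration wording with a statement that two patches are given, the second at 09.00 the next day.
- Protocol Synopsis, Safety endpoints and Adverse events, and SAP 24c: define the non-fatal SAE limit as the later of 48 hours after patch 1 or 24 hours after patch 2 is applied. Apply the same limit to the listed events for consistency.
- SAP Table 8: relabel the left panel so that non-fatal SAEs are shown to the day 2 limit and only fatal SAEs to day 90.

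Minimum capture after patch 2 rises from 15 to 24 hours; the range becomes 24 to 39 hours and is not equalised. The cost is up to 9 hours more collection for those first treated before 09.00 and none for anyone else, a window of 48 to 57 hours from patch 1 in place of a common 48, and wording changes by amendment with whatever approval that requires. The regimen does not change.
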